#### **Nodular PR**

Persistent bone marrow nodules on bone marrow biopsy in patients achieving a CR or PR. Lymphoid aggregates should be evaluated with immunohistochemistry to determine whether they are comprised of CLL cells, lymphocytes other than CLL cells, or T cells. If nodules are not composed of CLL cells, a CR can be documented provided all other criteria are met.

#### **Progressive disease (PD)A**

At least one of these criteria must be documented:

- The appearance of a newly enlarged lymph node ( $>1.5 \text{ cm}$ ), splenomegaly, hepatomegaly, or other organ infiltration.
- An increase of 50% or more in size of a previously involved site (e.g., lymph nodes, spleen, or liver) measuring  $\geq 1.5 \text{ cm}$ .
- An increase of 50% or more in the total circulating lymphocyte count with absolute lymphocyte count of  $5000/\text{microL}$  ( $5 \times 10^9/\text{L}$ ) or greater.◊
- Richter's transformation documented by lymph node or other tissue biopsy.
- Development of neutropenia, anemia, or thrombocytopenia attributable to **CLL**.§

#### **Stable disease**

Patients who do not meet the criteria for a complete remission, partial remission, or progressive disease, have stable disease. Stable disease is therapeutically equivalent to a nonresponse (i.e., refractory disease).

For patients treated with a therapy for a defined treatment duration, response assessment should be performed at least two months after the completion of therapy. For those receiving continued therapies or treatment strategies that include a maintenance phase, response assessment should be performed at least two months after achieving "maximum response" defined as a treatment phase where no additional improvement is seen during at least two months of therapy.

CLL: chronic lymphocytic leukemia; SLL: small lymphocytic lymphoma; ANC: absolute neutrophil count.

\* These include  $\geq 10\%$  unintentional weight loss within the previous six months, fatigue that interferes with work or usual activities, fevers greater than  $100.5^{\circ}\text{F}$  ( $>38^{\circ}\text{C}$ ) for  $\geq 2$  weeks, or night sweats for  $>1$  month.

¶ Assessment of residual CLL cells in the bone marrow for this purpose is not based on flow cytometry.

Assessment for measurable residual disease (MRD, also called 'minimal residual disease') is reserved for clinical trials. Although bone marrow biopsy is required to confirm a CR, it is not always recommended in general practice as it may not impact management. If the above clinical and hematologic parameters are compatible with a CR and the clinician chooses not to perform a bone marrow biopsy, the documented response can be "partial remission."

Δ Transient increases in lymph node size may occur during treatment with novel inhibitors and should not be considered PD.

◊ For patients treated with therapies that may cause lymphocytosis (e.g., kinase inhibitors), an increase in blood lymphocyte count, by itself, does not uniformly indicate an increased tumor burden, but may reflect redistribution of leukemia cells from lymphoid tissues. In such cases, increased lymphocytosis alone is not a sign of treatment failure or progressive disease.

§ Cytopenias cannot be used to determine disease progression during active therapy since they may be due to administered cytotoxic agents. Cytopenias that occur at least three months after the completion of therapy and are accompanied by an infiltrate of clonal CLL cells on bone marrow biopsy can be used to define disease progression. Specific values that define progression include a decrease in hemoglobin level by more than 2 g/dL (20 g/L) or to less than 10 g/dL (100 g/L) or a decrease in platelet count by more than 50% or to less than 100,000/microL ( $100 \times 10^9/L$ ).

### **6.3.3 Response Criteria – Splenic Marginal Zone Lymphoma([121](#))**

Partial response: 50% or greater decrease in spleen size. A reduction in previously enlarged nodes (if present) by at least 50% with no increase in the size of any single lymph node and no new enlarged lymph nodes. An increase of <25% in a lymph node <1.5 cm is not considered significant. In addition to the above two criteria, one of the following hematologic parameters must be met in order to qualify for a PR:

- Platelet count  $\geq 100,000/\text{microL}$  ( $100 \times 10^9/L$ ) or at least 50% improvement over baseline (if this value was abnormally low at baseline).
- Hemoglobin concentration  $\geq 12 \text{ g/dL}$  (110 g/L) or 50% improvement over baseline (if this value was abnormally low at baseline) without red blood cell transfusions or erythropoietin support.

Complete response: Resolution of organomegaly, normalization of the blood counts (Hb $>12 \text{ g/dL}$ ; platelets  $>100,000/\mu\text{L}$  and absolute neutrophil count  $> 1500 / \mu\text{L}$  and no evidence of circulating clonal B cells). No evidence or minor BM infiltration detected by immunohistochemistry.

No response: Patients who do not meet the criteria for a complete remission, partial remission, or progressive disease, have stable disease. Stable disease is therapeutically equivalent to a nonresponse (i.e., refractory disease).

Progressive disease: At least one of these criteria must be documented:

- The appearance of a newly enlarged lymph node ( $>1.5 \text{ cm}$ ), splenomegaly, hepatomegaly, or other organ infiltration.
- An increase of 50% or more in size of a previously involved site (e.g., lymph nodes, spleen, or liver) measuring  $\geq 1.5 \text{ cm}$ .
- Development of neutropenia, anemia, or thrombocytopenia attributable to **SMZL**.

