### 6.3 RESPONSE CRITERIA

In general, response rate will be assessed according to the Lugano response criteria for FL, MCL and MZL; and the International Workshop on Chronic Lymphocytic Leukemia (iwCLL) criteria for CLL. Notable exceptions are mentioned below.

- iwCLL criteria may also be used for MCL when the disease involves peripheral blood, bone marrow or spleen without significant lymphadenopathy.
- Separate response criteria for splenic marginal zone lymphoma as proposed by Matutes et al.([121](#))
- For patients with MALT lymphoma of the ocular adnexa, an MRI based response criteria will be used in conjunction with ophthalmologic evaluation.([122](#))
- Group d'Etude des Lymphomes de l'Adult (GELA) grading system to define the histologic response of gastric MALT lymphoma will be utilized for gastric marginal zone lymphoma of MALT type.([123](#))

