### 6.3.2 Response Criteria – CLL

The response rate in CLL patients will be calculated based on iwCLL response criteria (Hallek et al 2018)(90):

| Complete remission (CR)  |
|--|
| Requires all of the following criteria:   |
| 

• Absolute lymphocyte count <math><4000/\text{microL}</math> (<math>4 \times 10^9/\text{L}</math>).

• No lymph nodes <math>>1.5</math> cm in diameter.

• No hepatomegaly or splenomegaly.

• No constitutional symptoms attributable to CLL.*

• Bone marrow recovery as demonstrated by ANC <math>>1500/\text{microL}</math> (<math>1.5 \times 10^9/\text{L}</math>), platelet count <math>>100,000/\text{microL}</math> (<math>100 \times 10^9/\text{L}</math>), and hemoglobin concentration <math>>11 \text{ g/dL}</math> (110 g/L) in the absence of transfusion or growth factor support.

• Bone marrow at least normocellular for age, without evidence for typical CLL lymphocytes by morphologic criteria and immunohistochemistry and without nodular lymphoid aggregates.†

 |
| CR with incomplete bone marrow recovery (CRi)  |
| Fulfills all requirements for CR except has persistent neutropenia, anemia, or thrombocytopenia thought to be unrelated to the disease and likely related to drug toxicity. These patients must have a normal bone marrow aspirate and biopsy with no evidence of clonal infiltrates.  |
| Partial remission (PR)   |
| At least two of these criteria must be documented:  |
| 

• A decrease in the peripheral absolute lymphocyte count by at least 50% from the level prior to therapy.

  |

- A reduction in previously enlarged nodes by at least 50% with no increase in the size of any single lymph node and no new enlarged lymph nodes. An increase of <25% in a lymph node <1.5 cm is not considered significant.
- A decrease in the size of the liver and/or spleen by at least 50%.

One of the following hematologic parameters must be met in addition to two of the above criteria in order to qualify for a PR:

- Platelet count  $\geq 100,000/\text{microL}$  ( $100 \times 10^9/\text{L}$ ) or at least 50% improvement over baseline (if this value was abnormally low at baseline).
- Hemoglobin concentration  $\geq 11 \text{ g/dL}$  ( $110 \text{ g/L}$ ) or 50% improvement over baseline (if this value was abnormally low at baseline) without red blood cell transfusions or erythropoietin support.

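### The splenic MZL partial-response hemoglobin limit is printed as 12 g/dL and as 110 g/L, which are different values; a narrow group of patients is classified differently by each

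*Combined protocol and SAP*

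**What the plan says.** Section 6.3 assesses FL, MCL and MZL by the Lugano criteria in general, with listed exceptions. One exception is "Separate response criteria for splenic marginal zone lymphoma as proposed by" a cited source, and Section 6.3.3 sets those criteria out.

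PR there needs a spleen reduction of at least 50%, the node criterion (where nodes were enlarged), and a blood-count condition: "one of the following hematologic parameters must be met in order to qualify for a PR". The two parameters are:

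- **Platelets:** at least 100,000/µL, "or at least 50% improvement over baseline (if this value was abnormally low at baseline").
- **Hemoglobin:** at least 12 g/dL, followed by a bracket and an alternative route, "110 g/L) or 50% improvement over baseline", again for a value that was low at baseline, and without red-cell transfusion or erythropoietin support.

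Complete response in the same section asks for "Resolution of organomegaly, normalization of the blood counts". It defines the hemoglobin part as above 12 g/dL and gives no SI figure.

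The CLL criteria in Section 6.3.2 have a parallel PR line. Its threshold is 11 g/dL (110 g/L), "or 50% improvement over baseline (if this value was abnormally low at baseline) without red blood cell transfusions or erythropoietin support".

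**The concern.** The two figures in the hemoglobin line are meant to be one value in two units, and they are not. This is an operative rule rather than background text.

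- PR counts toward ORR, a secondary endpoint (Sections 1.1.2 and 10.1.2), reported by cohort and histology with 95% confidence intervals (Section 10.4.3).
- The first date on which PR criteria are met starts DOR (Section 6.3.6.2).
- PR after six triplet cycles leads to six more (Sections 3.1.1 and 3.1.2). A patient without at least PR stops therapy (Section 1.2.1).

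Two assessors who each follow the printed text could therefore classify the same patient differently. If that surfaces only after data are in hand, the threshold would have to be chosen with the outcome known.

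**Working it through.** **Step 1: the plan's own pair.** The formula is g/L = 10 × g/dL.

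- 12 g/dL × 10 = 120 g/L; the plan prints 110 g/L.
- 110 g/L ÷ 10 = 11 g/dL; the plan prints 12 g/dL.
- Gap: 120 − 110 = 10 g/L, or 1 g/dL.

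The pair does not reproduce.

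**Step 2: is this a habit of the document?** The other hemoglobin pairs in the neighboring criteria all convert. CLL complete and partial remission use 11 g/dL (110 g/L). The CLL progression footnote uses 2 g/dL (20 g/L) and 10 g/dL (100 g/L). Only the splenic MZL pair fails, and no other section restates or corrects it.

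**Step 3: who is affected?** The Section 6.3.3 rule is: spleen AND nodes AND (platelets OR hemoglobin), where each blood count can pass on its absolute value or on a 50% rise from a low baseline. The invented patients below all have unsupported hemoglobin of 11.5 g/dL and meet the node criterion. They were classified at each limit, with a baseline below the relevant limit treated as low.

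| Pattern | Spleen met | Platelets now (baseline), /µL | Baseline Hb, g/dL | PR at 12 g/dL | PR at 11 g/dL |
|---|---|---|---|---|---|
| a | yes | 150,000 (120,000) | 10 | yes | yes |
| b | yes | 80,000 (50,000), +60% | 10 | yes | yes |
| c | yes | 80,000 (70,000), +14% | 7.5, rise 53% | yes | yes |
| d | no | 80,000 (70,000) | 10 | no | no |
| e | yes | 80,000 (70,000), +14% | 10, rise 15% | **no** | **yes** |

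Only pattern e depends on which figure is used.

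**Step 4: can pattern e occur under the entry criteria?** Section 2.1.1.7 requires hemoglobin ≥9 g/dL and platelets ≥50,000, with transfusions permitted for both.

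- *Hemoglobin 50% route.* A result below 12 g/dL can be a 50% rise only from a baseline below 12 ÷ 1.5 = 8.0 g/dL (for a result of 11 g/dL, 11 ÷ 1.5 = 7.3 g/dL). From the entry floor, 9 × 1.5 = 13.5 g/dL, already above both limits. This route therefore rescues almost nobody in the disputed band, unless a pre-transfusion value serves as baseline, as in pattern c.
- *Platelet routes.* A patient may enter below 100,000. From 70,000, a 50% rise means 105,000, so 80,000 fails both platelet routes.

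Pattern e is therefore possible, though nothing in the documents says how often it would arise.

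**Step 5: size on the ORR scale.** Section 2.3.2.1 caps the MZL expansion cohort at 6. If all 6 are evaluable and one is in pattern e, the shift is 1/6 = 16.7 points. The denominator is an assumption. With 3 evaluable patients the shift is 1/3 = 33.3 points. If, for example, 6 same-dose MZL patients from Cohort 2 were added, it is 1/12 = 8.3 points. With no affected patient it is zero.

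**The case against.** The best reply is that this is a slip in a parenthesis. The protocol leads with g/dL for its hemoglobin limits, the study is run at a single institution, and complete response in the same section uses 12 g/dL. The bracket also matches the CLL value, so it may have been carried over. A reader might infer that 12 g/dL is plainly meant and nothing is unclear. That is plausible, but it remains an inference. The text prints both figures, and a borrowed CLL line with only one number edited would look the same whichever number was intended.

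A second reply concerns reach, and it largely stands. A reader might infer that response is undefined for every patient with hemoglobin between 11 and 12 g/dL. The documents do not support that. Only one blood-count parameter is needed, each has a 50% route, and the spleen and node criteria apply first, so four of the five patterns above come out the same under either figure. The criteria also cover splenic disease only, one of three MZL subtypes (Section 1.2.2). The number of splenic patients is not projected and could be zero.

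A third reply is that ORR is secondary, is assessed in a preliminary way (Section 10.2) with no test attached, and uses best response (Section 6.3.6.1), so a borderline visit may be overtaken by a clearer one. This too is fair for ORR. It does not remove the effect on the DOR start date or on the decision taken after Cycle 6.

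**Conclusion.** The line is wrong as written: its two figures differ by 10 g/L and cannot both be the threshold. The consequence is confined to a splenic MZL patient who meets the spleen and node criteria, fails both platelet routes, has hemoglobin of 11.0 to below 12.0 g/dL without transfusion or erythropoietin, and has no qualifying 50% hemoglobin rise. For that patient, PR, and with it ORR, DOR and continuation after Cycle 6, turns on the figure chosen.

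The 16.7-point shift is conditional on six evaluable MZL expansion patients with exactly one affected. It is not an expected bias, and it should not be read as a shift in the trial's overall response rate. Evaluability (Section 10.3.2) and possible pooling with Cohort 2 (Section 10.2) leave the denominator open. The primary safety endpoint, DLT rules, stopping rules and sample size do not depend on this line. This is a minor but definite correction.

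**What to change.** In Section 6.3.3, reconcile the two hemoglobin figures against the splenic MZL criteria that Section 6.3 cites, and print one threshold with g/dL and g/L in agreement. Adding the SI value to the complete-response line would make the two rules easy to compare. Carry the reconciled figure into any response worksheet or case report form that uses it.

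Do this before splenic MZL responses are assessed. If any have been assessed already, record which figure was applied and whether either reading changes the result. This review does not say which value is right. The cost is one figure in one line, with no effect on visits, sample size or analysis methods.

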### **6.3.4 Response Criteria – MALT lymphoma of the ocular adnexa([122](#))**

Partial Response: 50% or greater reduction in the maximum diameter of the lesion from its original tumor size on imaging (CT/MRI) or ophthalmologic evaluation.

Complete Response: Complete resolution of the lesion on imaging (CT/MRI) or ophthalmologic evaluation.

### 6.3.5 Response Criteria - Gastric MZL of MALT type

| Response (score) | Description                       | Histological Characteristics  |
|------------------|-----------------------------------|---|
| CR               | Complete histological remission   | Normal or empty LP and/or fibrosis with absent or scattered plasma cells and small lymphoid cells in the LP, no LEL                       |
| pMRD             | Probable minimal residual disease | Empty LP and/or fibrosis with aggregates of lymphoid cells or lymphoid nodules in the LP/MM and/or SM, no LEL                             |
| rRD              | Responding residual disease       | Focal empty LP and/or fibrosis with dense, diffuse or nodular lymphoid infiltrate, extending around glands in the LP, focal LEL or absent |
| NC               | No change                         | Dense, diffuse or nodular lymphoid infiltrate, LEL usually present  |

LEL, lymphoepithelial lesions; LP, lamina propria; MM, muscularis mucosa; SM, submucosa.

### 6.3.6 Definitions

#### 6.3.6.1 Best Overall Response

The best overall response rate (ORR) is the best response recorded from the start of the treatment until disease progression/recurrence (taking as reference for progressive disease the smallest measurements recorded since the treatment started).

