#### 1.1.2 Secondary Objectives

- To determine the best overall response rate (CR + PR) of triplet combination therapy with magrolimab, obinutuzumab, and venetoclax
- To determine the rate of complete molecular remission (MRD negativity) by flow cytometry or similar assays as they become available in patients after triplet combination therapy with magrolimab, obinutuzumab, and venetoclax (in CLL patients only)
- To determine the duration of response (DOR) of triplet combination therapy with magrolimab, obinutuzumab, and venetoclax
- To estimate progression-free survival (PFS), event-free survival (EFS), and overall survival (OS) of triplet combination therapy with magrolimab, obinutuzumab, and venetoclax

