#### **4.1.3 Infectious prophylaxis for Pneumocystis Jiroveci**

As mentioned in Section [1.2.6.2.1.2](#), patients with MZL who received obinutuzumab based therapy had a higher rate of Grade 3-5 AEs compared to patients with FL, including a higher rate of infections. All adult subjects with MZL will receive prophylaxis for Pneumocystis Jiroveci during study therapy administration. Trimethoprim/sulfamethoxazole 1 DS tablet by mouth on Monday, Wednesday, and Friday is the preferred schedule. Subjects allergic to either component may receive inhaled pentamidine 300 mg once a month or other standard treatments.

Prophylaxis will begin with initiation of treatment (Cycle 1, Day 1 of dose-finding or Cycle -2, Day 1 of dose expansion) and will be stopped upon completion of therapy unless continued administration beyond this point is deemed necessary based on inadequate immune reconstitution. The use of antibiotics and/or anti-viral prophylaxis according to institutional guidelines is also allowed.

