### 6.3.6.8 Objective Tumor Response Rate

The proportion of patients who achieve at least a partial response (PR) to therapy.

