#### **10.1.2 Secondary Endpoints**

- Overall response rate (ORR = CR+PR) after triplet combination therapy with magrolimab, obinutuzumab, and venetoclax
- Complete molecular remission rate (CMR) by flow cytometry or similar assays as they become available in patients after triplet combination therapy with magrolimab, obinutuzumab, and venetoclax (in CLL patients only)
- Duration of response (DOR)
- Event-free survival (EFS)
- Progression-free survival (PFS)
- Overall survival (OS)

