### **10.3.2 Evaluable for Objective Response**

Only those patients who have measurable disease present at baseline, have received at least one cycle of treatment (magrolimab+obinutuzumab) therapy, and have had their disease re-evaluated will be considered evaluable for response. (NOTE: Patients who exhibit objective disease progression after receiving at least one cycle of magrolimab+obinutuzumab will also be considered evaluable.)

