### **10.4.9 Exploratory Analyses**

The following are the exploratory analyses planned:

- Overall response rate (ORR) after doublet-combination therapy with magrolimab and obinutuzumab

- Complete molecular remission rate (CMR) by ctDNA assay or similar assays as they become available after doublet-combination therapy with magrolimab and obinutuzumab
- Complete molecular remission rate (CMR) by ctDNA assay or similar assays as they become available after triplet-combination therapy with magrolimab, obinutuzumab and venetoclax
- Lead time for ctDNA assay in detecting molecular relapse prior to clinical progression
- Identify potential biomarkers and molecular correlates that are associated with response and/or resistance to the study treatment
- Test immunogenicity of magrolimab and asses the effect of anti-drug antibodies (ADA) on the pharmacokinetics, pharmacodynamic markers, efficacy, and safety of magrolimab.

The ORR and CMR rates will be determined and reported from individual cohorts and histological diagnosis. Responses will also be reported with waterfall plots, when appropriate. The exploratory objectives such as seeking to identify potential biomarkers and molecular correlates that are associated with response and/or resistance to the study treatment, will be assessed using descriptive statistics as well as non-parametric methods such as exact Wilcoxon rank sum tests. The analyses will be done without formal adjustment for multiple comparisons, but in the context of the number of tests performed.

Magrolimab PK data will be summarized using summary statistics (mean, median, range, standard deviation, etc.) at each time point. The overall rate of ADA occurrence and type of ADA (e.g., transient vs persistent) will be summarized for all patients. PK in ADA positive and negative patients will be tabulated at each timepoint. If relevant, the impact of ADA occurrence on efficacy and safety will be assessed through summary statistics.

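### In expansion Cohorts 3-6, the best-response definition in 6.3.6.1 does not fit the secondary endpoint of ORR after the triplet: it shuts out triplet responses that follow a window PD and can admit responses seen only on the doublet

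*Combined protocol and SAP*

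**What the plan says.** **Endpoint.** The secondary objective (1.1.2) is the best overall response rate of the triplet. The secondary endpoint (10.1.2) is "Overall response rate (ORR = CR+PR) after triplet combination therapy with magrolimab, obinutuzumab, and venetoclax". A separate exploratory analysis (10.4.9) is "Overall response rate (ORR) after doublet-combination therapy with magrolimab and obinutuzumab". The plan therefore treats the two rates as different quantities.

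**Definition.** Section 6.3.6.1 gives best overall response, with the abbreviation ORR, as "the best response recorded from the start of the treatment until disease progression/recurrence". It names no regimen and makes no provision for the window.

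**Start of treatment.** Section 4.1.3 ties the start of Pneumocystis prophylaxis to "initiation of treatment (Cycle 1, Day 1 of dose-finding or Cycle -2, Day 1 of dose expansion". Appendix G, footnote 11, likewise describes the window as two cycles of treatment and schedules CT at its end, before venetoclax.

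**Window progressors.** Sections 3.1.2 and 3.10.1 allow a patient with PD in the window to go straight on to the triplet.

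**Evaluable set.** Under 10.3.2, patients with measurable disease who "have received at least one cycle of treatment (magrolimab+obinutuzumab) therapy, and have had their disease re-evaluated will be considered evaluable for response". Venetoclax is not required. The note adds: "Patients who exhibit objective disease progression after receiving at least one cycle of magrolimab+obinutuzumab will also be considered evaluable".

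**Analysis.** Section 10.4.3 reports ORR and CR rate by cohort and histology with 95% confidence intervals. It has no rule for window responses or window PD.

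**The concern.** The endpoint concerns the triplet, but the only definition bearing its label starts two cycles before the third drug and stops at the first progression. Two kinds of expansion patient are then scored in a way that does not answer the question:

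- A patient who progresses on the doublet, moves to the triplet as the protocol provides, and then responds. The response comes after the definition has closed, yet the patient stays in the denominator.
- A patient who responds only in the window. Venetoclax is conditional on the Table 9 criteria, and Tables 16 and 17 limit delays in the window, so such a patient may never receive it and still be counted in a triplet rate.

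At stake is the meaning of the reported triplet ORR and CR rate, which are the main clinical response results of cohorts of 6 to 18 patients.

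**Working it through.** **1. Sample sizes (10.2).** Dose-finding: 6 + 6 + 6 + 6 = 24 at most. Expansion: 18 FL + 6 MZL + 12 MCL + 6 CLL = 42. Total: 24 + 42 = 66, which agrees with the plan. No ORR target, power or test is stated, so there is no such figure to reproduce.

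**2. Patient paths in Cohorts 3-6.**

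| Path | 6.3.6.1 read literally | ORR after the triplet |
|---|---|---|
| CR/PR in the window, still present at an evaluation after C1D1 | responder | responder |
| First CR/PR after C1D1, no window PD | responder | responder |
| CR/PR in the window only, whether or not venetoclax was given | responder | non-responder |
| Window PD with no earlier response, then triplet, then CR/PR | non-responder | responder |
| No CR/PR at any time | non-responder | non-responder |

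Only the third and fourth rows differ. Section 3.6.1 lets some patients continue treatment beyond PD but does not say how a later response is scored, so it does not settle the fourth row.

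**3. Effect of one patient.** With the denominator fixed at n, one change of status moves ORR by 1/n:

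- FL: 1/18 = 5.6 points
- MCL: 1/12 = 8.3 points
- MZL or CLL: 1/6 = 16.7 points

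Section 10.2 permits pooling with dose-finding patients at the same dose. If 6 such patients join, Cohorts 1 and 3 give 1/(6+18) = 1/24 = 4.2 points. Cohorts 2, 4, 5 and 6 taken together give 1/(6+6+12+6) = 1/30 = 3.3 points. In dose-finding, C1D1 is already the start of treatment, so the problem does not arise there.

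**4. Assumed example, FL, n = 18.** The documents give no rate for either affected path. Suppose 12 patients are responders under 6.3.6.1. Let w be the number who responded only in the window and p the number who responded on the triplet after a window PD, each between 0 and 3.

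- As written: 12/18 = 66.7% whatever w and p are (exact 95% CI 41.0 to 86.7%).
- Scored after C1D1, all 18 in the denominator: (12 − w + p)/18.

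| w | p | Result |
|---|---|---|
| 2 | 0 | 10/18 = 55.6% (30.8 to 78.5%) |
| 0 | 2 | 14/18 = 77.8% (52.4 to 93.6%) |
| 3 | 0 | 9/18 = 50.0% |
| 0 | 3 | 15/18 = 83.3% |
| 2 | 2 | 12/18 = 66.7%, but with two different patients counted |

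- Among patients given venetoclax, if none of the w received it: (12 − w + p)/(18 − w). For w = 2, p = 0 this is 10/16 = 62.5%; for w = 2, p = 2 it is 12/16 = 75.0%.

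**5. Why the PD reference must be stated.** Section 6.3.6.1 judges PD against the smallest measurements since treatment started. In a window progressor that minimum predates the window PD. A lesion shrinking on the triplet could still measure as PD against it at the first scan after C1D1, and scoring would close again at once.

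**The case against.** The strongest reply is that 6.3.6.1 is generic. Section 1.1.3 uses the same term for the two-cycle doublet, and 10.1.2 and 10.4.9 attach it to one regimen each. Read with its endpoint, a patient never given venetoclax has no response after the triplet. The evidence that the clock starts at Cycle -2 comes from a prophylaxis section and a scan footnote, neither of which defines an endpoint. This stands in part: it shows what the plan intends and softens the window-only direction. It does not help the window progressor, because the definition's closing point is explicit and no passage reopens it.

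It is also fair to say that the effect may be nil. Both patient types could be absent, the two effects can cancel, and a 5.6-point shift lies well inside the interval for 12/18. Section 10.2 sizes expansion by expected accrual and treats response as preliminary. That limits the weight of the point but does not make the definition fit.

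Two stronger readings should be resisted:

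- **Rival definitions.** A reader might infer that 6.3.6.8 ("The proportion of patients who achieve at least a partial response (PR) to therapy") is a competing rule giving a second ORR from the same data. The documents do not support this. That section is silent on progression rather than ruling on it, and its label, objective tumor response rate, is not used in the objectives, endpoints or analyses. It neither conflicts with 6.3.6.1 nor resolves the problem.
- **Wrong denominator.** A reader might infer that 10.3.2 is itself in error. Keeping doublet progressors in the denominator is conservative. What is missing is how they, and patients never given venetoclax, enter the numerator.

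**Conclusion.** The point holds for ORR and CR rate in Cohorts 3-6. Applied as written, 6.3.6.1 excludes triplet responses after a window PD and can include responses seen only on the doublet, so it does not measure ORR after the triplet. The exclusion follows directly from the text. The inclusion also rests on reading the start of treatment as Cycle -2 Day 1, which 4.1.3 and Appendix G support indirectly.

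The size is known only per patient, as computed above. A reader might infer that the plan inflates the triplet ORR. The documents give no basis for a direction: window-only responses raise the rate, excluded triplet responses lower it, and neither frequency is given. A window responder still in response after C1D1 counts either way.

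Nothing here touches the DLT evaluation, the dose decision or the stopping rules. PFS and EFS run from enrolment, are clearly stated, and are not part of this point.

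**What to change.** **6.3.6.1 and 10.4.3.** Define triplet ORR and CR rate as the best response at any evaluation after C1D1 until the first PD after C1D1, with the original pre-treatment baseline as the reference for CR and PR. Include scheduled follow-up evaluations. A list ending at Cycle 12 or end of treatment would be too narrow: Appendix G schedules CT in follow-up, and the CLL criteria in 6.3.2 call for assessment at least two months after fixed-duration therapy, whereas the post-Cycle 12 CT falls at 21 to 28 days.

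State that a window PD does not end triplet response scoring. In window progressors, judge later PD against the smallest measurements from the scan showing the window PD (or the pre-C1 scan, if done) onward.

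**10.3.2.** Keep all response-evaluable expansion patients as the denominator, with those never given venetoclax counted as non-responders. Add the rate among those given at least one venetoclax dose as a supplement, noting that it conditions on reaching C1D1.

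**Reporting.** Give the number of triplet responders already in CR or PR at the pre-C1 scan, since scoring after C1D1 does not by itself separate carry-over from the doublet. Keep window ORR as the exploratory doublet result.

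**Cost.** Wording and slightly more reporting, with no new scans. A progressor moved on at once may lack a pre-C1 scan, in which case the scan showing the window PD serves as the PD reference. The rule should be fixed before response data are summarised.
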